2.1 Study Design

[figure not shown]
This is an observational, retrospective cohort study. Eligible patients will be identified from the Syapse Learning Health Network database and medical chart review will be conducted by Syapse Certified Tumor Registrars (CTRs). All study data are secondary data and will have been collected retrospectively from existing clinical data originally collected as part of routine care. This single-arm descriptive analysis will describe the patient characteristics, clinical attributes and treatment patterns of A/MBC patients with HR+/HER2- disease, who were treated with palbociclib + AI as first-line therapy. Additionally, clinical effectiveness outcomes for these patients will be evaluated between Feb 2015 and July 2019.

Study population

The study will include adult patients 18 years or older, diagnosed with HR+/HER2- A/MBC who initiated palbociclib combination therapy with AI as the first-line therapy on or after 03 February 2015 up to and including 31 July 2019. Patients for this study will be identified from the Syapse Learning Health Network database.

Preliminary analysis identified up to 1,074 patients with evidence of key primary inclusion criteria: breast cancer diagnosis and palbociclib treatment. Three to four hundred patients are expected to fulfil complete study inclusion criteria. Given the inclusion criterion requiring a qualifying treatment identification period between 03 February 2015 through 31 July 2019, and assuming a data cutoff date of 01 February 2020, the minimum follow-up available is therefore 6 months.

PFIZER CONFIDENTIAL

Data source

Patients will be identified and data will come from the Syapse Learning Health Network database which includes both inpatient and outpatient clinical and molecular data captured through manual abstraction and interoperative data feeds from a number of health system source systems, including:

- *Electronic medical record (EMR), including inpatient, outpatient oncology, ambulatory, surgical, etc.*
- *Electronic data warehouse (EDW)*
- *Laboratory information system (LIS)*
- *Picture archiving and communication system (PACS)*
- *Hospital based cancer registries*
- *Computerized physician order entry (CPOE)*

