- *Additionally, Syapse augments health system data with the Surveillance, Epidemiology, and End Results (SEER) national cancer registry, other regional registries, the Social Security Death Index (SSDI), digitized obituary data. In order to capture complete and accurate vital status and dates of death, Syapse brings together data from multiple sources to create a composite view of patients' mortality (including EHR, hospital registry, manual abstraction, digital obituaries (such as tributes.com and legacy.com), Social Security Death Index, and SEER). Syapse is in the process of validating the completeness and accuracy of the Syapse mortality composite score versus the National Death Index (NDI), a centralized database of death records. Initial analysis shows that the combined Syapse Data Sources are very accurate. More detailed information forthcoming in the data management document.*

Treatment/cohort labels

Data from patients with only one treatment group labelled as palbociclib + AI are explored in this retrospective study.

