of the 2nd line for patients with >1 line of therapy, date of last contact, or end of study period.

- Real world time to treatment discontinuation (rwTTD)- It is defined as length of time from the start of palbociclib + AI treatment to the earliest of the following: date the patient discontinues first-line treatment, date of death, last known usage of first-line treatment, or end of study period.
- Real world time to next treatment (rwTTNT)- It is defined as length of time from the start of palbociclib + AI treatment to the earliest of the following: subsequent line of therapy initiation, date of death, date of last contact, or end of the study period.
- Real world time to chemotherapy (rwTTC)- It is defined as length of time from the start of palbociclib + AI treatment to the earliest of the following: the day before the start of subsequent chemotherapy for patients with evidence of chemotherapy, or date of death for any reason. Or, where censored, the latest of date of last contact, or end of the study period.
- Real world time to dose adjustment (rwTTDA)- It is defined as length of time from the start of palbociclib + AI treatment to the earliest of the following: date of first-line treatment dose adjustment, date of death, date of first-line treatment discontinuation, date of last contact or end of study period.

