Kaplan-Meier survival analysis is used to descriptively characterize time to event outcomes. In this study, following time to event outcomes will be analyzed-

- Time to Real-world overall survival (rwOS)

[figure not shown]
The time origin for analysis of rwOS is start of the first-line therapy, and the terminal event is death. For patients not known to be deceased at the time of analysis, rwOS will be censored at the earliest of the last date of last contact or the end of the study period.

- Time to Real-world progression-free survival (rwPFS)

The time origin for analysis of rwPFS is start of the first-line therapy. Patients without a clinician-assessed progression event or death will be censored at the earliest of the following events: date of initiation of the 2nd line for patients with >1 line of therapy, date of last contact, or end of study period.

- Real world time to treatment discontinuation (rwTTD)

PFIZER CONFIDENTIAL

The time origin for analysis of rwTTD is start of the first-line therapy. Patients without first-line treatment discontinuation and who did not die will be censored at the earliest of the following events: last known usage of first-line treatment, or end of study period.

- Real world time to next treatment (rwTTNT)

The time origin for analysis of rwTTNT is start of the first-line therapy. Patients without a subsequent line of therapy initiation and who did not die will be censored at the earliest of the following events: date of last contact, or end of the study period.

- Real world time to chemotherapy (rwTTC)

The time origin for analysis of rwTTC is start of the first-line therapy. Patients who did not receive subsequent chemotherapy and who did not die will be censored at the latest of the following events: date of last contact, or end of the study period.

- Real world time to dose adjustment (rwTTDA)

The time origin for analysis of rwTTDA is start of the first-line therapy. Patients without a first-line treatment dose adjustment will be censored at the earliest of the following events: first-line treatment discontinuation, date of death, date of last contact, or end of the study period.

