9.2 APPENDIX 2: Description of data elements used in the study

The following data elements will be extracted from feeds and/or curated by Certified Tumor Registrars (CTRs) for this study:

Data Elements	Description
Demographic characteristics	
Date of birth	Year, month, day (Availability of the exact date will depend on the Expert de-ID approach)
Date of initial BC diagnosis	Date of initial breast cancer (BC) diagnosis
Date of A/MBC diagnosis	Date of advanced/metastatic breast cancer (A/MBC) diagnosis
Patient sex	Male, Female, Transsexual, Other, Not Provided
Primary race	American Indian/Alaska Native; Asian; Black/African American/Native Hawaiian/Pacific Islander; White; Not Provided; Other (Exact list will depend on the expert de-ID approach)
Secondary race	(if provided) (Exact list will depend on the expert de-ID approach)
Ethnicity	Non-Hispanic/Non-Latino; Hispanic/Latino; Unknown (Exact list will depend on the expert de-ID approach)
Region of residence	Northeast, Midwest, South, West Captured at A/MBC diagnosis (Exact list will depend on the expert de-ID approach)
Insurance type	Medicare/Medicaid; Commercial; Commercial and Medicare/Medicaid; None; Not Provided Captured at 1) date of A/MBC diagnosis; and 2) at initiation of palbo
Menopause status	Premenopausal; Postmenopausal; Perimenopausal; Unknown; Not applicable. Captured on date closest to but before: 1) A/MBC diagnosis; and 2) initiation of palbo

PFIZER CONFIDENTIAL

	
Menopausal status: captured if explicitly stated in clinician notes. Otherwise captured based on following definition of menopause from NCCN Guideline v.3.2019:
 
Prior bilateral oophorectomy (date of surgery)
 
Age >=60 years old
 
Age <60 years old and amenorrheic for 12 months+ in the absence of chemotherapy, tamoxifen, toremifene, or ovarian suppression.
 
Additionally, type, name, and start/end date of ovarian suppression agent is captured

Date of death	If patient vital status = deceased, date of death from the medical record (capturing from EMR, registries, third party integrations) (Availability of the exact date will depend on the Expert de-ID approach)
Last contact date	If patient is alive (not deceased), date of the last contact by a healthcare provider from the medical record (Availability of the exact date will depend on the Expert de-ID approach)
Clinical characteristics	

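### Time to chemotherapy (rwTTC) is censored at the later of last contact and study end, so patients lost to follow-up count as chemotherapy-free to the cutoff and rwTTC is overstated

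*SAP*

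**What the plan says.** Section 7.2 (Objective 2, rwTTC) reads: "Patients who did not receive subsequent chemotherapy and who did not die will be censored at the latest of the following events", followed by date of last contact and end of study period. The definition in Section 5.1 agrees: "Or, where censored, the latest of date of last contact, or end of the study period". Appendix 2 (Section 9.2) repeats that wording.

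In the same part of Section 7.2, time to next treatment is handled the other way on the same two dates: "Patients without a subsequent line of therapy initiation and who did not die will be censored at the earliest of the following events". For overall survival, "rwOS will be censored at the earliest of the last date of last contact or the end of the study period". The rules for rwPFS, rwTTD and rwTTDA also take the earliest of their listed dates. No reason is given for treating rwTTC differently.

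Appendix 2 defines last contact, for patients who are alive, as the "date of the last contact by a healthcare provider from the medical record". For mortality, Section 2.1 says "Syapse brings together data from multiple sources to create a composite view of" vital status, drawing on registries, the Social Security Death Index and obituaries as well as health records. It describes nothing comparable for chemotherapy.

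**The concern.** Kaplan-Meier estimation requires that time at risk be time under observation. A chemotherapy start can be seen only while the patient is in contact with a contributing health system. Under the rwTTC rule, a patient who leaves stays in the risk set with no possibility of a chemotherapy event being recorded. Risk sets are inflated and the curve is held up.

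The rule also conflicts with the SAP's other endpoints. Death is an rwTTC event, yet a patient censored at last contact for rwOS because later survival is unknown is treated as known alive to study end for rwTTC. The same patient leaves the rwTTNT analysis at last contact, although starting chemotherapy would normally open a new line. The rwTTC and rwTTNT curves therefore cannot be compared.

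rwTTC is listed among the primary endpoints in Section 5. The rule affects its quartiles, the landmarks from 3 to 36 months, the 125 mg starting-dose subgroup and the Cox model. The Kaplan-Meier error lengthens time to chemotherapy, which flatters the regimen, and a single-arm study has no comparator in which it could cancel.

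**Working it through.** **Calendar (Section 2.1).** Index dates run "on or after 03 February 2015 up to and including 31 July 2019". The SAP adds: "assuming a data cutoff date of 01 February 2020, the minimum follow-up available is therefore 6 months".

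- Shortest potential follow-up: 31 Jul 2019 to 01 Feb 2020 = 185 days; 185 / 30.4375 = 6.08 months. This reproduces the SAP's 6 months.
- Longest: 03 Feb 2015 to 01 Feb 2020 = 1,824 days; 1,824 / 30.4375 = 59.9 months.

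**One patient.** Index 03 Feb 2015, last contact at 12 months, no event recorded.

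- rwOS and rwTTNT: min(12, 59.9) = 12 months.
- rwTTC: max(12, 59.9) = 59.9 months.
- Unobserved time counted as event-free: 59.9 − 12 = 47.9 months.

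This is the extreme index date; later entrants have less time to be carried.

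**Whole cohort: assumptions not in the SAP.** Exponential time to chemotherapy or death with median m; total hazard λ = ln 2 / m, split into chemotherapy λc and death λd; independent loss at hazard γ = −ln(1 − annual loss) / 12; uniform entry over the index window. For 5%, 10% and 20% annual loss, γ = 0.00427, 0.00878 and 0.01860 per month.

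Under the SAP rule every non-event is carried to study end, so the Kaplan-Meier curve tends to one minus the probability that an event has been recorded by t:

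- Deaths unseen after loss: S(t) = 1 − [λ/(λ+γ)] × [1 − exp(−(λ+γ)t)]
- Deaths still found after loss: S(t) = exp(−λd·t) × {1 − [λc/(λc+γ)] × [1 − exp(−(λc+γ)t)]}

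Example: m = 30, 10% loss, deaths unseen. λ = 0.02310, λ+γ = 0.03189 and λ/(λ+γ) = 0.7246. At 36 months S = 1 − 0.7246 × (1 − 0.3173) = 0.505; the true value is 0.5^(36/30) = 0.435. The median solves 0.5 = 0.7246 × (1 − e^(−0.03189t)), giving t = 36.7 months against a true 30.

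Results for m = 30 with 40% of the hazard being death (true 36-month value 43.5%):

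| Annual loss | Deaths after loss | Median, SAP rule | 36-month event-free, SAP rule | Median, earlier date (simulated) |
|---|---|---|---|---|
| 0% | – | 30.0 | 43.5% | 30.0 |
| 5% | found | 31.4 | 45.4% | 29.5 |
| 10% | found | 33.0 | 47.2% | 28.8 |
| 20% | found | 36.8 | 50.6% | 27.9 |
| 5% | unseen | 32.8 | 47.1% | 30.0 |
| 10% | unseen | 36.7 | 50.5% | 30.1 |
| 20% | unseen | 55.8 | 56.9% | 30.0 |

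A simulation of 400,000 patients per scenario gave SAP-rule medians within 0.3 months of these.

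**Other true medians.** In the simulation, the smallest overstatement with loss was 24.9 against a true 24 months (5% loss, deaths found). The largest was a median not reached against a true 40 months (20% loss, deaths unseen). For a true median of 36 months with deaths unseen, the formula gives 40.1 and 46.4 months at 5% and 10% loss, and a median beyond the 59.9-month window at 20%. The 36-month estimates are 53%, 56% and 62% against a true 50%. With 30% of the hazard being death and deaths found, the medians are 38.5, 41.4 and 49.5 months.

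**The case against.** The strongest reply concerns size. The SAP states no loss rate, so every magnitude is a scenario, and with no loss the two rules agree. The larger figures also assume that deaths after last contact are missed, whereas Section 2.1 describes composite mortality capture meant to find them. That is fair: the rows with deaths found are the more natural reading, and there the median is overstated by about 1 to 7 months for a true median of 30. The bias remains because chemotherapy after last contact is still unseen. Loss is also expected, since Table 15.4.5 lists leaving the health system as a reason for discontinuation.

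Second, the Cox model is less exposed than the curves. If loss is unrelated to the covariate, hazard ratios are only slightly attenuated. In one run with a true hazard ratio of 1.5 and 10% annual loss, the estimate was 1.45 under the earlier date and 1.41 under the later. Material distortion needs loss that differs by covariate.

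Third, moving to the earlier date does not by itself give an unbiased estimate. Section 7.2 censors only patients who did not die, so a death found after last contact stays an event while survivors are censored at last contact. In the table this pulls the median down by 0.5 to 2.1 months. This stands and belongs in the fix.

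Fourth, the study is descriptive, without hypotheses, and one of six time-to-event endpoints is affected. That limits the reach of the error but does not defend the rule. Whether the wording was intended cannot be settled from the SAP and does not matter: a programmer following any of the three places would implement the later date.

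**Conclusion.** The rule is wrong as written and must be corrected. It counts unobserved time as chemotherapy-free, contradicts the SAP's treatment of the same patients for rwOS and rwTTNT, and has no stated rationale. The direction is certain for the Kaplan-Meier curve whenever follow-up is lost: rwTTC is too long.

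The size is conditional on exponential event times, independent loss of 5% to 20% a year and the assumed share of deaths. For a true median of 30 months the overstatement is about 1.4 to 7 months if deaths are found after loss, and about 3 to 26 months if they are not. The actual figure cannot be known until loss to follow-up is tabulated.

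End of study period is itself not fixed to a date. Section 2.1 gives an assumed cutoff of 01 February 2020 but also describes outcome evaluation between February 2015 and July 2019. Patients lost before study end are carried past last contact under either reading. Under the second, patients seen after July 2019 would also be censored later than study end.

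**What to change.** 1. In Sections 5.1 and 7.2 and in the rwTTC entry of Appendix 2, censor patients with neither subsequent chemotherapy nor death at the earlier of last contact and end of study period, as for rwTTNT.
2. State how a death found after last contact is handled for rwTTC, because keeping it as an event while censoring survivors at last contact biases the estimate slightly downward. A sensitivity analysis under the alternative handling would show whether it matters.
3. Give end of study period one explicit date.
4. Re-run the rwTTC Kaplan-Meier, landmark, 125 mg subgroup and Cox outputs, and report how many event-free patients had last contact before study end.

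The cost is one word in three places, two clarifying sentences and a re-run of one endpoint. The Introduction says italicised text comes directly from the protocol, and the Appendix 2 entry is italicised, so the protocol wording should be checked too. The reported rwTTC will probably become less favourable. The SAP's amendment section shows that a censoring rule (for rwPFS) has already been amended at the manuscript stage.

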 - c. Real-world time to treatment discontinuation (rwTTD) from the start of the first-line therapy at time points 3, 6, 12, 18, 24, 30, and 36 months.
 - d. Real-world time to next treatment (rwTTNT) from the start of the first-line therapy at time points 3, 6, 12, 18, 24, 30, and 36 months.
 - e. Real-world time to chemotherapy (rwTTC) from the start of the first-line therapy at time points 3, 6, 12, 18, 24, 30, and 36 months.
 - f. Real-world time to dose adjustment (rwTTDA) from the start of the first-line therapy at time points 3, 6, 12, 18, 24, 30, and 36 months.

5.1 Definitions/Derivations for Demographic, Clinical characteristics, treatment pattern and Efficacy/Effectiveness Endpoint(s)

- Age at initial diagnosis, A/MBC diagnosis, at start of palbociclib treatment and death. - They will be categorized into age categories: <50, 50-64, 65 –74, ≥75 years.
- Time to metastasis- It is defined as months between initial and metastasis diagnoses. It will be categorized into ≤12 months, 13-24 months, 25-36 months,>36 months and de novo metastatic.
- Disease Free Interval (DFI)- It is defined as months from the end of adjuvant therapy to the date of disease recurrence. It will be categorized into ≤12 months, 13-24 months, 25-36 months,>36 months and Unknown.
- Line of therapy- The line number (1; 2; 3; etc.) in the A/MBC setting will be assigned based on Syapse line of therapy algorithm.
- Regimen medication(s)- Systemic therapies included in line regimen defined by Syapse line of therapy algorithm.
- Time to first dose change- It is defined as days from palbo dose 1 start date to palbo dose 2 start date, if applicable.
- Number of dose changes- Number of dose reduction(s) and number of dose increases over the calendar time (quarter since February 2015) and over treatment cycle since palbo dose 1 start date.
- Real-world Overall Survival (rwOS)- It is defined as length of time from the start of palbociclib + AI treatment to the earliest of the following: date of death, date of last contact, or the end of study period
- Real-world progression free survival (rwPFS)- It is defined as length of time from the start of palbociclib + AI treatment to the earliest of the following: clinician-assessed progression event (sources include medical oncology consult/note, radiation oncology note and discharge summary), date of death, date of initiation

PFIZER CONFIDENTIAL

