7 STATISTICAL METHODOLOGY AND STATISTICAL ANALYSES

7.1 Statistical methods

Descriptive analyses: For categorical variables (eg region, race, and stage at initial diagnosis), data will include the frequency (number of cases) and percentage (%) of total patients observed in each category; for continuous variables (eg age and time from initial breast cancer diagnosis to metastatic diagnosis), variables will be presented as the mean, standard deviation (SD), median, 25th and 75th percentiles and ranges (minimum and maximum) in some cases. The calculation of percentages will always include the missing category in the case of missing values. Continuous variables may be categorized into intervals, with the distribution of patients (N, %) provided.

Kaplan-Meier curves and landmark analyses will be performed to estimate rwPFS, rwOS, rwTTD, rwTTC, rwTTDA and rwTTNT. Specifically, landmark time points are; 3, 6, 12, 18, 24, 30, and 36 months for rwPFS and 6, 12, 18, 24, 30, and 36 months for rwOS. For rwTTD and rwTTNT, landmark time points are; 3, 6, 12, 18, 24, 30, and 36 months. Ninety-five percent confidence intervals on the median rwPFS, rwOS, rwTTD, rwTTNT, rwTTC and rwTTDA will be reported.

Cox proportional hazard models may include age categories, race, ECOG performance, menopausal status, stage at initial diagnosis, time from initial diagnosis to metastatic diagnosis, metastatic status (De novo, versus number of metastatic sites), number of disease sites (1, 2, ≥ 3), prior endocrine therapy, prior chemotherapy, prior surgery, prior radiation therapy, bone-only disease, presence of visceral disease, and presence of brain metastases as appropriate based on availabilities of the data and sample sizes. Potential interactions may be examined using survival trees for time to events.

All data analysis will be executed using statistical software R version 3.6.1 or later.

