7.2 Statistical Analyses

Objective1:

- a. To describe the demographic and clinical characteristics for patients diagnosed with HR+/HER2- A/MBC.

[figure not shown]
The numbers of breast cancer patients in the Syapse database meeting the eligibility criteria will be presented in an attrition table.

Demographic and clinical characteristics variables that will be reported include age, sex, race, insurance status, menopausal status, and region of residence at A/MBC diagnosis, stage of initial diagnosis, histology, Eastern Cooperative Oncology Group (ECOG) performance status (where ECOG score unavailable, Karnofsky performance status will be converted to corresponding ECOG score) and comorbid disease burden, HER2 and estrogen receptor (ER)/ progesterone receptor (PR) status, BRCA status, number and sites of distant metastasis at A/MBC diagnosis; modalities of treatment received prior to A/MBC diagnosis (chemotherapy, hormone therapy, surgery, radiation therapy), disease free interval (time between completion of adjuvant therapy and diagnosis of A/MBC) and follow-up time in the study. Descriptive analysis methods as detailed in Section 7.1 will be used for summarizing these parameters as appropriate.

- b. To describe the treatment patterns for patients diagnosed with HR+/HER2- A/MBC.

Treatment patterns generally include the record of all systemic anti-cancer therapies received from the index date through the end of the study period.

CCI

Description will include each of the following.

- Distribution of regimens, with the frequency and percentage of patients receiving each regimen within each line from the diagnosis of A/MBC through the end of the record.
- Description of sequence of regimens across lines, which shows how individual regimens were sequenced across lines through the end of the record of systemic therapy. Description will include the frequency and percentage of patients who received each specific sequence of treatments.
- Description of the dosing will include the starting dose, end dose, dose adjustment (dose increase and dose reduction), type of dose adjustment (dose modification, schedule changes, dose delay or hold), discontinuation reason (including death, progression, end of planned therapy, insurance changes, schedule change, dose delay, hold, cost, patient refusal, toxicity), and time to dose adjustment.

Objective2:

To examine clinical effectiveness for patients diagnosed with HR+/HER2- A/MBC.

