One Kaplan-Meier analysis is generated for each time to event endpoint. Kaplan-Meier analysis will include number of patients with events and censored patients, median, 25th percentile and 75th percentile times to event (in months), 95% CI of the quartiles and ranges (minimum and maximum). Kaplan-Meier analysis will be repeated in the subgroup of patients who received a starting dose of 125mg.

One Cox regression analysis will be generated for each time to event endpoint, provided the sample size supports the analysis. Demographic and baseline clinical characteristics, some examples are detailed in section 7.1, will be included to the extent that sample size permits. Results from this analysis results will include parameter estimates, p-values, standard errors, hazard ratios and 95 % CIs of hazard ratios. The proportional hazards assumption will be assessed graphically with the inspection of Schoenfeld residuals and by including interaction terms between the variables and log(time).

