Figure 15.2.5.5. Kaplan-Meier Analysis of time to rwTTC for Patients who Received 125mg Starting Dose

Real world time to Dose Adjustment

Table 15.2.6.1. Kaplan-Meier Analysis of time to rwTTDA from Start of 1L Using Regimen-Based Lines of Therapy

Figure 15.2.6.2. Kaplan-Meier Analysis of time to rwTTDA

Table 15.2.6.3. Cox Model for Assessing Factors Associated with time to rwTTDA from Start of 1L

Table 15.2.6.4. Kaplan-Meier Analysis of time to rwTTDA from Start of 1L Using Regimen-Based Lines of Therapy for Patients who Received 125mg Starting Dose

Figure 15.2.6.5. Kaplan-Meier Analysis of time to rwTTDA for Patients who Received 125mg Starting Dose

Note-Each efficacy outcome will be analyzed as per the timepoints defined in section 5.

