Therapy start date	Year, month, day
Therapy end date	Year, month, day
Start reason	Recurrence; Progression; Other reason not related to worsening disease
Start reason source date	Year, month, day (can be linked to clinician confirmation date of recurrence/progression if start reason is recurrence/progression)
Stop reason	Categories including: Progression; Toxicity; End of planned therapy; Insurance changes; Treatment ongoing; Other
Stop reason source date	Year, month, day (can be linked to clinician confirmation date of recurrence/progression if stop reason is recurrence/progression)
Treatment part of clinical trial	Yes; No
Palbociclib-specific variables (captured in addition to above variables)	
Combination AI partner	Letrozole, Anastrozole, Exemestane
Concomitant LHRH Agonists	Goserelin (Zoladex), Histrelin (Vantas), Leuprolide (Eligard, Lupron), Triptorelin (Trelstar)
Dose 1 (start dose)	125mg, 100mg, 75mg
Dose 1 start date	Year, month, day
Dose n (where n>=2)	125mg, 100mg, 75mg
Dose n start date	Year, month, day
Dose n adjustment type or reason	Categories include schedule change; dose delay; hold; cost; patient refusal; toxicity

Variables that will be derived from curated data will include the following:

Data Elements	Description
-----------------------------	---------------------------

PFIZER CONFIDENTIAL

Age at A/MBC diagnosis	Age in years; age categories: <50, 50-64, 65 –74, ≥75 years (Exact list will depend on the expert de-ID approach)
Age at start of palbociclib treatment	Age in years; age categories: <50, 50-64, 65 –74, ≥75 years
Date of death	If patient vital status = deceased, date of death from the medical record (capturing from EMR, registries, third party integrations) (Availability of the exact date will depend on the Expert de-ID approach)
Palbo dose change ever	Yes; No
Disease Free Interval (DFI)	Months from the end of adjuvant therapy to the date of disease recurrence ≤12 months, 13-24 months, 25-36 months >36 months Unknown
Endocrine sensitivity	≥12 months without recurrence/progression after completion of endocrine therapy in the adjuvant setting

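### Time to dose adjustment is censored at first-line discontinuation and at death and then estimated by Kaplan-Meier, which overstates the share of patients adjusted

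*SAP*

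**What the plan says.** SAP Section 7.2 (Objective 2) is the only text that says which rwTTDA end dates are events and which are censoring: "Patients without a first-line treatment dose adjustment will be censored at the earliest of the following events: first-line treatment discontinuation, date of death", followed by last contact and end of study. Section 5.1 lists the same dates without assigning status: "date of first-line treatment dose adjustment, date of death, date of first-line treatment discontinuation, date of last contact or end of study period".

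The estimator is set in Section 7.1: "Kaplan-Meier curves and landmark analyses will be performed to estimate rwPFS, rwOS, rwTTD, rwTTC, rwTTDA and rwTTNT". Section 7.2 asks for the "median, 25th percentile and 75th percentile times to event (in months), 95% CI of the quartiles". Section 5 fixes the landmarks: "Real-world time to dose adjustment (rwTTDA) from the start of the first-line therapy at time points 3, 6, 12, 18, 24, 30, and 36 months". The note closing Section 8.2.1 confirms them: "Note-Each efficacy outcome will be analyzed as per the timepoints defined in section 5". The SAP names no cumulative incidence function or other competing-risk method.

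Appendix 2 (Section 9.2) defines rwTTDA differently. It replaces discontinuation and last contact with the last known use of first-line treatment.

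**The concern.** Censoring is meant for patients whose outcome is still possible but unobserved. A patient who has stopped first-line treatment or died has left the risk set for good. Kaplan-Meier nevertheless treats that patient as someone who could still be adjusted at the same rate as those remaining on treatment. The landmark figures then no longer estimate the proportion of patients who had an adjustment, which is the natural quantity in a study meant to describe real-world treatment patterns.

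rwTTDA also stands apart from its siblings. Under Section 7.2, death is an event for rwOS, rwPFS, rwTTD, rwTTNT and rwTTC. Only rwTTDA censors it, and no reason is given.

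The end-date conflict is a separate fault in the same definition. For a patient with no recorded stop, Sections 5.1 and 7.2 count time at risk up to last contact, while Appendix 2 ends it at last known first-line use. Section 7.2 also uses last known use to censor rwTTD. Programmers working from different sections would get different results.

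**Working it through.** The SAP states no expected rate for rwTTDA, so there is no planned figure to reproduce. The direction follows from algebra. The size needs assumptions.

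**Direction.** At each adjustment time, with d1 adjustments among R at risk, one minus Kaplan-Meier rises by S_KM × d1/R. The Aalen-Johansen cumulative incidence (CIF) rises by S_all × d1/R, where S_all is the probability of being free of adjustment, discontinuation and death. Since S_all ≤ S_KM, one minus Kaplan-Meier is never below the CIF. It is strictly above once any adjustment follows a competing event. In 60 simulated cohorts of 300 to 400 patients, with adjustment and stopping times negatively, not or positively dependent, none of 420 landmark comparisons went the other way.

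**Inputs for the size.**
- From the SAP: 300 to 400 patients and minimum follow-up of 6 months (Section 2.1); landmarks of 3 to 36 months (Section 5).
- Assumed: one minus Kaplan-Meier at 12 months, p = 25 to 45%; median time to discontinuation or death, M = 15 to 25 months; share f of the first-year adjustment hazard falling in months 0 to 6. f = 0.5 is a constant hazard; 0.8 and 0.9 are front-loaded.

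**Formulas.** d = ln 2/M; H = −ln(1−p); a1 = fH/6 in months 0 to 6; a2 = (1−f)H/6 afterwards.
- 1−KM(t) = 1 − exp(−A(t)), where A is the cumulative adjustment hazard.
- For t > 6: CIF(t) = a1/(a1+d) × (1 − e^(−6(a1+d))) + e^(−6(a1+d)) × a2/(a2+d) × (1 − e^(−(a2+d)(t−6))). For t ≤ 6: the first term with t in place of 6.

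**Central case (p = 0.35, M = 20).** H = 0.4308 and d = 0.03466. For f = 0.5, a1 = a2 = 0.03590.

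| f | 12 mo: 1−KM vs CIF | 24 mo | 36 mo | KM median (mo) | Share ever adjusted |
|---|---|---|---|---|---|
| 0.5 | 35.0 vs 29.1% | 57.7 vs 41.5% | 72.5 vs 46.9% | 19.3 | 50.9% |
| 0.8 | 35.0 vs 30.8% | 45.3 vs 36.4% | 53.9 vs 39.5% | 30.3 | 43.3% |
| 0.9 | 35.0 vs 31.3% | 40.4 vs 34.2% | 45.3 vs 36.0% | 48.5 | 38.7% |

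In the two front-loaded rows Kaplan-Meier gives a median although fewer than half of patients would ever be adjusted. The 25th percentile moves less: 8.0 vs 9.6, 5.0 vs 5.6 and 4.5 vs 4.9 months (KM vs CIF).

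**Excess of 1−KM over CIF across the assumed range, in percentage points.**

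| f | 3 mo | 12 mo | 24 mo | 36 mo |
|---|---|---|---|---|
| 0.5 | 0.3–0.9 | 3.6–9.5 | 10.8–23.0 | 18.7–33.1 |
| 0.8 | 0.4–1.4 | 2.5–6.8 | 5.7–13.3 | 9.8–20.1 |
| 0.9 | 0.5–1.5 | 2.2–6.0 | 3.8–9.4 | 6.1–13.5 |

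**Yardstick.** With no censoring, the 95% half-width 1.96 × √(p(1−p)/n) runs from 4.7 points (p = 0.35, n = 400) to 5.7 (p = 0.50, n = 300).

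**The case against.** The strongest reply is that the SAP never calls these landmarks proportions of all patients. It says openly that follow-up ends at discontinuation, so the curve can be read as adjustment among patients still on treatment. That reading is legitimate as a net quantity, but only if stopping is independent of adjustment, and the SAP neither labels the result this way nor states the assumption. The assumption is doubtful, because the listed reasons overlap. For stopping, Section 7.2 gives "discontinuation reason (including death, progression, end of planned therapy, insurance changes, schedule change, dose delay, hold, cost, patient refusal, toxicity". For dose adjustment, Appendix 2 gives: "Categories include schedule change; dose delay; hold; cost; patient refusal; toxicity". The overlap should not be overstated: the stop-reason field in Appendix 2 names toxicity but not cost or refusal. Toxicity is the reason common to all the lists, and it alone makes independence implausible.

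Second, crude adjustment counts appear in Table 15.4.5, and numbers of events and censored patients accompany each Kaplan-Meier result. A careful reader could notice the gap, but these counts are not landmark-specific and do not correct the quantiles.

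Third, the half-width above is a best case. With the central case and assumed uniform follow-up of 6 to 60 months, the half-width is about 5.0 to 6.2 points at 12 months, against an excess of 3.7 to 5.9. At 24 months with f = 0.9 it is 5.7 to 6.6, against 6.1. At 36 months it is 7.1 to 9.7, against 9.3 to 25.7, with only about 11 to 28 patients still at risk. This stands: the bias is comparable to or below sampling error at 12 months, and clearly matters only later.

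Fourth, censoring competing events is valid for a cause-specific Cox model. That also stands. The fault lies in the proportions and quantiles, not the hazard ratios.

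**Conclusion.** The point holds. Read as the share of patients adjusted, one minus Kaplan-Meier under this censoring cannot be too low and will generally be too high, and the median and quartiles will be too early. This concerns the censoring rule only; unrecorded adjustments could pull the observed figure the other way. The size cannot be known from the SAP. Under the stated assumptions it is negligible at 3 months and can equal or exceed sampling error by 24 to 36 months. The conflict in end dates is real whatever the rates are. Section 3 sets no hypotheses or decision rules, so the consequence is a misleading description, not a wrong decision. The SAP should be changed, but the study does not depend on it.

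**What to change.** - Report the Aalen-Johansen cumulative incidence of dose adjustment, with 95% CI, at the Section 5 landmarks, treating first-line discontinuation and death as competing events.
- Censor patients with no adjustment, recorded discontinuation or death at the end of observed first-line dosing by one rule, for example the earliest of last known first-line use, last contact and end of study. State it identically in Section 5.1, Section 7.2 and Appendix 2.
- Label the rwTTDA Cox hazard ratios as cause-specific.
- Label any Kaplan-Meier result that is kept as hypothetical, assuming no discontinuation or death and independent censoring.

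The cost is SAP wording and one standard survival call in R, on dates already being collected. The one drawback is that the median may not be reached, in which case it should be reported as such.
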